	 To determine the prevalence of SARS-CoV-2 infections in 0 – 24 year olds, and variation in prevalence in time, age, ethnicity and geography (cross-sectional sero- epidemiological study) 	 Serum IgG to SARS-CoV-2 antigens, including spike protein and/or nucleocapsid (as measured by ELISA and/or neutralising assay)
	 To determine the kinetics of antibodies specific to SARS- CoV-2 following infection in a paediatric population (serial blood sampling in population sub-group) To determine relationship between serum and salivary antibodies against SARS-CoV-2 	 Serum IgG to SARS-CoV-2 antigens, including spike protein and/or nucleocapsid (as measured by ELISA and/or neutralising assay) Salivary IgG to SARS-CoV-2 antigens, including spike protein and/or nucleocapsid (as measured by ELISA)
Exploratory	 Comparison between recruitment strategies between groups The presence of SARS-CoV-2 virus in saliva in a sub-set of study participants 	 Representativeness of participants sampled, in terms of the local population's ethnicity, community identity, migrant population and socioeconomic background Differences in immunological read outs
	 To characterise T cell responses against SARS-CoV-2 in antibody seropositive and seronegative participants. 	 PCR for SARS-CoV-2 on saliva samples stored and processed at the end of the study.

 Humoral and cellular immunity against non SARS- CoV-2 coronaviruses 	 T cell responses to SARS-CoV-2 antigens including, but not limited to S, M and N proteins, as measured by techniques including, but not limited to ELISpot ICS Proliferation assay
	 Antigen specific IgG and T cells against non-SARS-CoV-2 coronaviruses (e.g. NL62 and 229E)

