Furthermore, in response to the outbreak of COVID-19 these samples will be used to look for changes in seropositivity to SARS-CoV-2 in England children +/- young adults through 2020/2021 (and beyond if necessary) as a marker of infection with this novel coronavirus. This is to support Public Health England in its SARS-CoV-2 seroprevalence work, with a goal of providing blood samples from 400 participants per month through 2020 as a repeat cross-sectional seroprevalence study. While the majority of participants will provide a single blood sample, a subset of participants will be enrolled into a longitudinal sampling cohort, providing up to a total of 4 blood samples (and 3 saliva samples) allowing analysis of the kinetics of rise and fall of SARS-CoV-2 specific antibody concentrations following SARS-CoV-2 infection, and the relationship between serum and saliva antibodies. This will in turn inform the interpretation of data from the repeat cross-sectional seroprevalence study. The 'repeat' blood samples collected as part of this study will be counted towards the study target of blood samples from a sub-set of participants. The longitudinal sampling cohort will comprise of both seropositive and seronegative participants.

The longitudinal cohort also provides an opportunity to address the knowledge gap regarding T cell responses to SARS-CoV-2 infections. At present, it is not clear how many people who are infected do not mount an antibody response and whether they have a detectable T cell response only. Commentary in the literature suggests that measuring antibody levels alone may underestimate population level immunity against COVID-19 (Sekine et al., 2020). The longitudinal cohort provides an opportunity to examine both T cell responses and the kinetics of this response.

There will be enhanced recruitment in Black, Asian and Minority ethnic (BAME) populations to develop an understanding on whether higher rates of disease in the BAME community are a result of

- o Greater exposure to COVID-19 contacts
- A higher likelihood of being infected once exposed
- o Greater risk of disease once infection occurs

Previous seroprevalence studies

Seroprevalence studies using residual sera

PHE has been utilising residual serum samples from participating laboratories across the country as part of its ongoing seroprevalence programme for many years. These samples are used as a serum bank for

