9.4. Screening and Eligibility Assessment

Given the low risk nature of the study there is no formal requirement for screening prior to the first study visit. However sites may choose to arrange contact with potential participants to discuss the study and a arrange clinic appointment or home visit. This is where exclusion criteria can be checked prior to arranging a visit.

Responses received from postcode districts not selected by PHE will not be eligible for group 1. Each postcode district has been selected based on sampling all quintiles of the IMD and to ensure representative data of the region.

In all groups, in order to ensure that there is a representative cohort from each age group multiple eligible participants from one household will only be eligible to take part if there are 5 years or greater between their ages.

During the study visit, the participant's eligibility will be assessed by a member of the study team. A brief medical history will be taken where participants will be asked about current health issues and medications as well as taking a vaccine history and personal and household history of respiratory/coronavirus infections from February 2020 onwards. Parents/legal guardians must have given written informed consent prior to an eligibility check being performed if the participant cannot consent for themselves. In these instances where the child is older than 11 years old there will be an assent form to complete.

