9.7. Laboratory methods

The blood samples obtained will be centrifuged, separated and frozen at local sites at -80 degrees Celsius. Ideally this will happen within 24 hours but there is a window of up to 72 hours. Shipping of sera to the laboratories of PHE will be as outlined in the Laboratory Analysis Plan. Residual sera not sent to PHE will be shipped to the Oxford Vaccine Group for storage and/or further analysis. For participants where consent is obtained for DNA extraction and storage in the Oxford Vaccine Centre biobank residual blood clots will be shipped to the Oxford Vaccine Group for this purpose.

Saliva samples with be processed in line with local SOPs.

Diphtheria

A multiplexed fluorescent bead assay will be used to quantify IgG antibodies to diphtheria toxoid, based upon previously published methodology (Pickering et al., 2002). For diphtheria, anti-toxin levels < 0.01IU/mL denote susceptibility, antitoxin levels 0.01 - 0.099 IU/mL provide basic protection, and antitoxin levels $\geq 0.1IU/mL$ are fully protective, as per the international standard (2009).

Group C Meningococcus

Serum bactericidal antibody (SBA) assays will be performed against the serogroup C target strain, C11 (phenotype C:16:P1.7-1,1) as previously described (Maslanka et al., 1997). The complement source that will be used in the SBA is pooled serum from 3-4 week old rabbits (Pel Freez Biologicals, WI USA). Titres will be expressed as the reciprocal serum dilutions yielding \geq 50% killing after 60 min. The lower limit of detection will be a titre of 4. Titres of <4 will be assigned a value of two for geometric mean titre (GMT) analysis. Titres of \geq 8 will be considered protective against MenC disease (Borrow et al., 2005).

Novel Coronavirus (SARS-COV-2)

Assays are currently under development by Public Health England and University of Oxford to measure:

- Concentrations of serum and saliva IgG specific to SARS-COV-2 spike proteins and/or nucleocapsid by ELISA
- SARS COV-2 Virion/pseudovirion neutralising activity.

T cell responses

T cell responses will be determined by measures including, but not limited to, ELISpot, Intracellular cytokine staining (ICS) and proliferations assays.

A pool of viral peptides such as S1, S2, M, N, ORF3, ORF1 will be used in ELISpot assays to measure T cell stimulation.

DNA storage

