- For prospectively collected samples where vaccination history is known, in individuals aged 12 -24 years, the proportion of individuals within each age band that have serum bactericidal titres of ≥8 to group C meningococcal disease, and whether SBA titres are associated with adolescent Men ACWY or MCC vaccine or not having received vaccine. Trends by age and differences by vaccination status will be assessed by Chi-squared of Fisher's exact test as well as by using logistic regression. Comparisons by geometric mean titres will also be done by t-tests or Kruskal Wallis as appropriate and by plotting geometric means with 95% confidence intervals by age groups.
- Across the whole age range (0-24 years) a comparison of proportions protected with previous seroprevalence studies carried out in 2009 and 1996 for diphtheria and 1996-99, 2002-4, 2009 and 2014 for Men C. This will be done by using all the samples and calculating prevalence within individual age bands with 95% confidence intervals and inferring differences based on non-overlapping 95% CIs which is conservative to allow for multiple testing when assessing many age bands.
- For all participants, a repeat cross-sectional analysis of the geometric mean titres (with 95% CI) of antibodies against SARS-CoV-2, and proportion (with 95% CI) of participants with anti SARS-CoV-2 antibodies above a (yet to be determined) threshold of 'positivity' throughout the study period
- For participants providing multiple serum samples, analysis of the proportion of participants who were initially seronegative who subsequently developed antibodies against SARS -CoV-2
- For participants providing multiple serum samples, analysis of the kinetics of the rise and fall of antibodies against SARS -CoV-2
- Calculation of the sensitivity and specificity of salivary antibody testing compared to serum.

Exploratory analyses

- Whether ethnicity, household income or other factors collected on the questionnaire are associated with antibodies against diphtheria and / or Men C and/or SARS-CoV-2. This will be done by multivariable logistic regression.
- Comparisons between groups 1 and 2 will be performed as detailed in study statistical analysis plan in terms of:
 - representativeness of ethnicity, community identity, migrant population and socioeconomic background of local communities
 - immunological end-points

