20%	20 (12.2, 27.8)	10 (0.2, 19.8)		individuals invited, for
30%	30 (21.0, 39.0)	20 (9.3, 30.7)	10 (0.0, 21.9)	representativeness will be
40%	40 (30.4, 49.6)	30 (18.7, 41.3)	20 (7.6, 32.4)	all individuals providing a sample and for
50%	50 (40.2, 59.8)	40 (28.6, 51.4)	30 (17.4, 42.6)	seroprevalence will all
60%	60 (50.4, 69.6)	50 (38.7, 61.3)	40 (27.6, 52.4)	individuals providing a
70%	70 (61.0, 79.0)	60 (49.3, 70.7)	50 (38.1, 61.9)	sample for which a laboratory result is

Table 5: Precision of estimates of change in prevalence with 100 samples at two time points.

obtained.

11.4. Group 3

Following discussions with Public Health England the suggested sample size would be 300 participants, with at least 100 from the Black/African/Caribbean/Black British community. This is based on preliminary data suggesting rates of seropositivity in adult males identifying as BAME are double that of the white community, and in those identifying as Black/ African/ Caribbean/Black British are 3 fold higher. Based on these proportions, and an estimate of 4% seropositivity in the white community, the above numbers would provide 80% power to detect similar differences in the paediatric populations.

The Level of Statistical Significance 11.5.

5% and 95% confidence intervals will be reported. For comparison across individual age bands for seroprevalence differences will be inferred based on non-overlapping 95% confidence intervals.

11.6. Procedure for Accounting for Missing, Unused, and Spurious Data.

The reason for missing data (consent withdrawn or unable to obtain any laboratory results) will be indicated. Missing data will not be imputed.

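### The objective is the prevalence of SARS-CoV-2 infection, but the stated analysis is the proportion above a positivity threshold, with no allowance for serum assay error

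*Protocol*

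**What the plan says.** The secondary objective in Protocol sections 3 and 6 is "To determine the prevalence of SARS-CoV-2 infections in" 0 to 24 year olds, and its variation by time, age, ethnicity and geography. The listed outcome is serum IgG by ELISA and/or neutralising assay. Section 5 treats seropositivity "as a marker of infection with this novel coronavirus".

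For this objective section 11.1 gives geometric mean titres and the "proportion (with 95% CI) of participants with anti SARS-CoV-2 antibodies above a (yet to be determined) threshold of" positivity. On the tests themselves, section 9.7 says: "Assays are currently under development by Public Health England and University of Oxford to measure" serum and saliva IgG and neutralising activity. Sensitivity and specificity appear once in the analysis section, for saliva, with serum as the reference.

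Section 11.2.2 does name one correction to the seroprevalence calculation, for over-sampling of participants positive at the first visit. It also treats the change in prevalence between two time points as incidence. Section 11.4 sizes Group 3 from "an estimate of 4% seropositivity in the white community" and from preliminary data that "rates of seropositivity in adult males identifying as BAME are double that of the white community", with a 3-fold rate in the Black/African/Caribbean/Black British community. Section 11.1 promises a detailed statistical analysis plan, which is not at hand.

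**The concern.** The target is infection and the stated estimator is a test result. The two agree only if the assay is close to perfect, and an assay still under development with an open cut-off cannot be presumed so. When few people have been infected, even a small false-positive rate supplies a sizeable share of all positives, while missed infections pull the other way.

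Three things are at stake: the reported level of infection in children, the age and ethnicity ratios (which false positives pull towards 1), and the confidence interval, which reflects sampling error only.

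**Working it through.** **Inputs.** From the protocol: planning rates of 4%, 8% (double) and 12% (3-fold), and Group 3 of 300 with at least 100 Black participants (section 11.4); 100 samples in each of 4 age bands per time point, so 400, and up to 3,500 participants in Groups 1 and 2 (section 11.2.2). Not in the protocol and therefore assumed: Se 0.80 to 1.00 and Sp 0.98 to 0.995, equal across groups; and the size of the white comparison group.

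**The plan's own figure.** The 80% power in section 11.4 cannot be reproduced uniquely because no comparator size is given. With an assumed 1,500 comparators and a two-sided 5% pooled-variance test of 4% against 8% (300 in Group 3):
- pooled rate (60 + 24)/1,800 = 0.0467; null SE = √[0.0467 × 0.9533 × (1/1,500 + 1/300)] = 0.01334
- alternative SE = √[0.04 × 0.96/1,500 + 0.08 × 0.92/300] = 0.01646
- power = Φ[(0.04 − 1.96 × 0.01334)/0.01646] = Φ(0.84) = 0.80.

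The same method for 4% against 12% with 100 participants gives 0.876. So 80% is attainable from Groups 1 and 2.

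**Observed against true prevalence.** Observed = p × Se + (1 − p) × (1 − Sp).

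| Se | Sp | True 4% reads as | True 8% reads as | Ratio (true 2) | False share of positives at 4% |
|---|---|---|---|---|---|
| 0.80 | 0.995 | 3.68% | 6.86% | 1.86 | 13% |
| 1.00 | 0.995 | 4.48% | 8.46% | 1.89 | 11% (0.48/4.48) |
| 0.90 | 0.99 | 4.56% | 8.12% | 1.78 | 21% |
| 0.80 | 0.98 | 5.12% | 8.24% | 1.61 | 38% |
| 0.90 | 0.98 | 5.52% | 9.04% | 1.64 | 35% |
| 1.00 | 0.98 | 5.92% | 9.84% | 1.66 | 32% (1.92/5.92) |

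For example, at 0.90/0.99: 0.04 × 0.90 + 0.96 × 0.01 = 0.0360 + 0.0096 = 0.0456. A true 3-fold ratio reads as 2.22 (at 0.80/0.98) to 2.78 (at 1.00/0.995).

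**Direction.** Net bias at 4% is zero when 1 − Se = (0.96/0.04) × (1 − Sp) = 24 × (1 − Sp). At Sp 0.995 that is Se 0.88. Below that sensitivity the crude figure is too low, above it too high.

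**Reading back from observed to true.** Rogan-Gladen: true = (observed + Sp − 1)/(Se + Sp − 1). At 0.90/0.99, observed 4% and 8% become 0.03/0.89 = 3.37% and 0.07/0.89 = 7.87%, a ratio of 2.33. At 0.90/0.98 they become 2.27% and 6.82%, a ratio of 3.00.

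**Change over time.** The false-positive floor cancels in a difference, but the observed change is (Se + Sp − 1) times the true change: 0.89 at 0.90/0.99 and 0.78 at 0.80/0.98.

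**The interval.** As an illustration with a constant true 4% and 0.90/0.98, 400 samples give 5.52% ± 1.96 × √(0.0552 × 0.9448/400) = 3.3% to 7.8%, which still covers 4%. With 3,500 the same formula gives 4.8% to 6.3%, which does not. At 0.90/0.99 and 3,500 it is 3.9% to 5.3%, which just covers it. The bias is thus hidden in a single round and shows, in the less specific case, once samples are pooled.

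**The case against.** The strongest reply is that this is detail for the statistical analysis plan. Section 11.1 never calls the proportion crude, rules out no correction and leaves the threshold open, and a test adjustment cannot be fully specified until assay and cut-off are chosen. Much of that stands: a reader might infer that the protocol fixes a crude estimate, and the text does not go so far. It does, however, state the estimator and one correction to it (over-sampling) while leaving out assay error, so the gap between target and estimator is in the protocol's own text.

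A second reply is that the proportion seropositive is a coherent estimate of seroprevalence. That is true, but the stated objective is infection.

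Three stronger readings are tempting and not supported:

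- **That Group 3 is underpowered.** With 1,500 comparators, reading 4% and 8% as true infection rates would lower power from 0.80 to 0.69 at 0.90/0.99, or 0.62 at 0.90/0.98. But section 11.4 states these rates as seropositivity, so they already contain assay error. On a similar assay power stays at 0.80, and it is the infection ratio that is understated.
- **That prevalence is always inflated.** The sign depends on assay figures the protocol does not give.
- **That all sera from before the questionnaire's window are known negatives.** Eligibility history covers "personal and household history of respiratory/coronavirus infections from February 2020 onwards", but that is a history-taking window and does not show that earlier sera were infection-free. Nor does the protocol say how many early sera exist or what volume remains, and section 9.1 caps first-stage recruitment.

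**Conclusion.** The point holds as a mismatch between objective and stated analysis. Near 4% prevalence, and under the assumed assay range, the stated proportion can lie from 0.3 points below to 1.9 points above the true infection prevalence, and a true doubling between groups would be reported as roughly 1.6 to 1.9. These sizes rest on assumed sensitivity and specificity and on equal assay performance across groups. The mechanism does not depend on those particular values. Section 5 itself notes that it is unclear how many infected people mount no antibody response, so the relevant sensitivity is against infection and may be lower than a laboratory figure. The Group 3 sample size is not shown to be wrong.

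**What to change.** In section 11.1, report crude seropositivity and, as the estimate of infection prevalence, a test-adjusted prevalence (Rogan-Gladen or an equivalent Bayesian estimate), with the uncertainty in sensitivity and specificity carried into the 95% interval. Give the sensitivity and specificity used and their source.

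Take specificity from assay validation data and, where numbers allow, from this study's own sera collected in 2019 only, run on the same assay. Recruitment was planned from July 2019 and section 2 already has Group 1 samples tested for both vaccine responses and SARS-CoV-2, so little extra testing should be needed. Do not use early-2020 sera as known negatives: any infected child among them would lower the estimated specificity and over-correct the prevalence.

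In section 11.4, state that the 4%, 2-fold and 3-fold figures are on the observed seropositivity scale.

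The cost is wording plus wider intervals: the standard error grows by 1/(Se + Sp − 1), which is 1/0.89 = 1.12 at 0.90/0.99, before uncertainty in Se and Sp is added. The adjustment removes bias but does not add power.

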11.2. Sample Size Determination

11.2.1: Group 1

The sample size for Group 1 is determined based on the primary objectives as well as the secondary objective to have a store of sera for future testing of immunity.

Historically serosurveys such as those done as part of the European Sero-epidemiology Network (ESEN) have had target sample sizes per age band of interest of 100-200. Age bands of interest have usually been one year bands until adult ages. For the purpose of this calculation this is taken as one year age bands to age 21 then a single band for 22-24 year olds. For the secondary objective 100 per age band will allow the precision of estimates of seroprevalence to be as given in table 2.

Table 2: Precision of seroprevalence estimates

Prevalence	95% CI Observed around the estimate with 100 per age band (2300 total)
10%	4.9-17.6
20%	12.7-29.2
30%	21.2-40.0
40%	30.3-50.3
50%	39.8-60.2
60%	49.7-69.7
70%	60.0-78.8
80%	70.8-87.3
90%	82.4-95.1

Precision will be improved when combining age bands for specific questions or when assessing trends by age for other secondary objectives. For example for diphtheria age bands of interest could be divided into <4,4-8,9-13,14-24 and for Men C into 0-10,11-12,13-15,16-19,20-24.

Focussing on the primary objectives

Representativeness of participants sampled

Within a study site representativeness is assessed by comparison to local population demographics. Each study region will have up to approximately 383 individuals allocated into Group 1. Overall all 2300 samples will be available for analysis in Group 1. With these numbers the precision of estimates of characteristics in the population and differences that would be significant to population data are given in Table 3. So, for example, if a specific ethnic group was 20% of the survey sample then in a region this would have a 95% Cl of 16.1-24.4% and would allow a proportion in the population of <14.3% or >26.6% to be detectable as different.

We will also compare our sample demographics with the population demographics of the corresponding NHS region. This will increase the sample size in some regions are there are multiple sites within that region.

	Re	gion (N=383)	Over	all (N=2300)	
Prevalence of	95% confidence	Prevalence below, above	95% confidence	Prevalence below,	
characteristic	interval	this in population that	interval	above this in population	
in sample		would significantly differ		that would significantly	
		(80% power, 5%		differ (80% power, 5%	
		significance, assuming		significance, assuming	
		population much larger		population much larger	
		than sample (>=10 fold))		than sample (>=10 fold))	
5%	3.0-7.7	2.3,9.1	4.1-6.0	3.8,6.5	
10%	7.2-13.5	6.0,15.3	8.8-11.3	8.2,12.0	
15%	11.6-19.0	10.0,21.0	13.6-16.5	12.9,17.3	
20%	16.1-24.4	14.3,26.6	18.4-21.7	17.6,22.5	
25%	20.7-29.7	18.8,32.0	23.2-26.8	22.4,27.7	
30%	25.5-34.9	23.3,37.3	28.1-31.9	27.2,32.9	

Table 3: Assessment of representativeness, precision and detectable differences

Comparison with residual samples

For comparison with the residual samples this is considered within age strata and is based on the 2017 data on residual samples for the numbers of residual strata by age. Due to the smaller number of residual samples in younger age groups (one of the key reasons for undertaking a community based seroprevelance survey), detectable differences are relatively large in those <4 years. In older age groups relatively, small differences can be detected in >4 year age bands. The example given below is for when the observed prevalence is 50% is the survey which is conservative as this gives the largest detectable differences.

Table 4: Comparison to residual samples by age strata with a total sample size of 2300

Age	Detectable difference from 50% (80% power, 5% significance)
<4	10.7
4 to 8	8.7
9 to 13	8.1
14 to 24	5.7
All Age	3.9

11.2.2: Group 1 and 2 combined

Sample size for SARS-COV-2 incidence based on change in prevalence

Across group 1 and 2 combined there will be over 3500 blood samples from 2800 to 3500 participants in total, at least 3200 of which will be from participants 19 years of age or younger. The intent of this is to obtain blood samples across 4 age bands (i.e. 100 in each of 0 -4 years, 5-9 years, 10-14 years, 15-19 years)to the end of the study. This will include sample taken from the longitudinal cohort, with seroprevalence calculations taking into account over-sampling of participants with positive SARS-Cov 2 antibodies at V1.

The table below shows the precision (95% CI) of estimates of change in prevalence (incidence) with 100 samples at each of two time points. For example with a prevalence of 10% at baseline and 30% at the next time point the incidence is 20% with 95% CI 9.3-30.7. The aim is to achieve 100 in each of 4 age groups at each time point.

Prevalence				
At next time				11.3. Analysis
point	0%	10%	20%	populations
10%	10 (4.1, 15.9)			 The analysis population for recruitment rates will be all
20%	20 (12.2, 27.8)	10 (0.2, 19.8)		individuals invited, for
30%	30 (21.0, 39.0)	20 (9.3, 30.7)	10 (0.0, 21.9)	representativeness will be
40%	40 (30.4, 49.6)	30 (18.7, 41.3)	20 (7.6, 32.4)	all individuals providing a sample and for
50%	50 (40.2, 59.8)	40 (28.6, 51.4)	30 (17.4, 42.6)	seroprevalence will all
60%	60 (50.4, 69.6)	50 (38.7, 61.3)	40 (27.6, 52.4)	individuals providing a
70%	70 (61.0, 79.0)	60 (49.3, 70.7)	50 (38.1, 61.9)	sample for which a laboratory result is

Table 5: Precision of estimates of change in prevalence with 100 samples at two time points.

obtained.

11.4. Group 3

Following discussions with Public Health England the suggested sample size would be 300 participants, with at least 100 from the Black/African/Caribbean/Black British community. This is based on preliminary data suggesting rates of seropositivity in adult males identifying as BAME are double that of the white community, and in those identifying as Black/ African/ Caribbean/Black British are 3 fold higher. Based on these proportions, and an estimate of 4% seropositivity in the white community, the above numbers would provide 80% power to detect similar differences in the paediatric populations.

The Level of Statistical Significance 11.5.

5% and 95% confidence intervals will be reported. For comparison across individual age bands for seroprevalence differences will be inferred based on non-overlapping 95% confidence intervals.

11.6. Procedure for Accounting for Missing, Unused, and Spurious Data.

The reason for missing data (consent withdrawn or unable to obtain any laboratory results) will be indicated. Missing data will not be imputed.

